5.2. Voruciclib Accountability and Compliance

The Principal Investigator or their representative will maintain detailed drug accountability records for all voruciclib provided by the sponsor. All voruciclib will be stored in a temperature-controlled (see [Section 5.3](#)), secure, locked location, and away from direct sunlight. The Principal Investigator shall maintain adequate records of the disposition of voruciclib, including dates, quantity, and use by subjects. Upon completion of the study, all remaining voruciclib will be accounted for and unused material will be returned to the Sponsor (or designee) using a traceable method (UPS, FedEx, etc.) or disposed of as otherwise instructed by the sponsor.

5.3. Storage of Voruciclib

The capsules and tablets should be protected from direct sunlight and stored in a cool place or at controlled room temperature, 15-25°C (59-77°F). Some US sites will store between 20-25°C (68-77°F) per investigational product label.

5.4. Storage of Venetoclax

Venetoclax will not be provided by the Sponsor. Venetoclax should be stored at or below 86°F (30°C) according to the US Prescribing Information ([Venclexta \[US Prescribing Information\] Rev 2022](#)).

6. ADVERSE EVENTS

6.1. Adverse Event (AE) Definition Using CTCAE V5.0

An AE is any untoward medical event that occurs to a subject following the start of voruciclib administration in monotherapy cohorts or the start of venetoclax in combination cohorts, whether or not the event is considered drug related. Pre-existing conditions are not considered an AE unless the condition worsens by at least one grade following the start of voruciclib administration in monotherapy cohorts or the start of venetoclax in combination cohorts.

Any drug-related AE of Grade 2 or higher should be followed for resolution until:

- The start of subsequent anti-cancer therapy or
- Subject discontinuation from the study or
- A new stable baseline or
- Death

Disease-related out-of-range laboratory values will not be considered AEs/SAEs if there is no change from the screening laboratory values, or if they are not deemed clinically significant by the Investigator.

6.2. Assessment of AEs

The Investigator will assess AEs for severity and relationship to voruciclib and to venetoclax and determine if an AE meets the criteria for an SAE. Each AE will be graded in the source documents using CTCAE v5.0.

6.3. Serious Adverse Event (SAE) Definition

An SAE is an AE that results in any of the following outcomes:

- Death
- A life-threatening condition
- An inpatient hospitalization or prolongation of an existing hospitalization
- A persistent or significant disability/incapacity
- A congenital anomaly/birth defect
- Important medical events that may not be immediately life-threatening or result in death or hospitalization but may jeopardize the patient or may require intervention to prevent one of the other outcomes listed above

Elective hospitalization not in response to an AE is not considered an SAE. Adverse events constituting an SAE will be reported beginning from the first dose of voruciclib, or venetoclax in the combination therapy group.

Disease progression, including death due to disease progression, is not considered an SAE.

6.4. Serious Adverse Event (SAE) Reporting

Serious adverse events will be captured from the first dose of voruciclib monotherapy or venetoclax in the combination regimen and continue to be captured until 30 days after the last dose of study drug(s), or until a subsequent anti-cancer therapy is initiated. SAEs occurring after 30 days will be captured if believed to be related to study drug.

All SAEs, regardless of drug attribution, must be reported to the Sponsor or designee within 24 hours of the Investigator becoming aware of the SAE. The SAEs must be reported in EDC; however, if EDC is not accessible, a paper SAE form must be submitted to the Medpace Safety email or fax number within 24 hours of being aware of the event. When the EDC system becomes available, all applicable SAE information must be entered in EDC. The designee, as listed below, will also be specified in the Study Manual.

To report an SAE, contact Medpace Clinical Safety as listed below:

Email: [contact]

[contact], Option 3 OR [contact], Option 3

[contact] OR [contact]

Sites must follow-up to confirm receipt of the SAE Report.

The Investigator must report new significant follow-up information for these events to the sponsor or designee immediately (i.e., no more than 24 hours after becoming aware of the information). New significant information includes the following:

- New signs or symptoms or a change in the diagnosis
- Significant new diagnostic test results
- Change in causality based on new information

- Change in the event's outcome, including recovery
- Additional narrative information on the clinical course of the event

SAEs must be reported by each site to the appropriate Institutional Review Board (IRB)/Independent Ethics Committee (IEC) in accordance with local reporting requirements.

Reporting requirements will also be based on the Investigator's assessment of causality and seriousness, with allowance for upgrading by the sponsor as needed.

Deaths within 30 days of the administration of voruciclib or the administration of combination therapy must be reported as an SAE unless the death is due to disease progression. Deaths occurring >30 days after the last dose of voruciclib or the last dose of combination therapy must be reported as an SAE if considered by the investigator as related to study drug(s).

The Investigator should make every effort to obtain and send death certificates and autopsy reports for all deaths to the sponsor.

In the event of a medical emergency (requiring immediate attention regarding operation of the clinical study and/or the use of study drug), study site staff will apply appropriate medical intervention according to current standards of care and contact the Medical Monitor or other designated sponsor representative.

6.5. Pregnancies

To ensure subject safety, each pregnancy in a subject on study treatment must be reported within 24 hours of learning of its occurrence; refer to [Section 6.4](#) and the study reference manual for reporting contact information. Study drug must be discontinued in a subject who becomes pregnant. The pregnancy must be followed for at least 3 months after term or spontaneous or voluntary termination to determine outcome including details of the birth, and the presence or absence of any birth defects, congenital abnormalities, or maternal and/or newborn complications.

Pregnancy is not an AE but should be recorded and reported by the Investigator to the Sponsor or Designee. Pregnancy follow-up should be recorded and should include an assessment of the possible relationship to the study drug of any pregnancy outcome. Any SAE experienced during pregnancy must be reported on the SAE Report Form.

Pregnancy outcomes must be collected for the female partners of any males who took study treatment in this study. Consent to report information regarding these pregnancy outcomes should be obtained from the mother.

Fertile male subjects, defined as all males physiologically capable of conceiving offspring, with female partners of childbearing potential must use condoms plus spermicidal agent during the study treatment period and for 90 days after the last dose of study drug, and should not father a child during this period.

Male subjects must also refrain from donating sperm during their participation in the study.

6.6. Relationship of Adverse Events to Study Treatment

The Investigator is obligated to assess the relationship between voruciclib or venetoclax and the occurrence of each AE. The Investigator is to use his/her best medical judgment in determining

the likely relationship of the AE to voruciclib or venetoclax. The relationship of an AE or SAE to voruciclib or venetoclax is to be classified as either ‘Related’ or ‘Not Related.’

7. RESPONSE ASSESSMENT

7.1. Response Assessment for Subjects with CLL/SLL

For subjects with CLL/SLL, efficacy assessments will be based on International Workshop on Chronic Lymphocytic Leukemia (IWCLL) criteria ([Halleck 2008](#)). Lymphocytosis may feature prominently during early treatment and can persist over time and should not be confused with disease progression in subjects with otherwise persistent disease control. Absent other objective evidence of disease progression, the occurrence of lymphocytosis will not preclude subjects from meeting the criteria for PR (if other criteria for PR are met) and will not be considered evidence of CLL/SLL progression if occurring in isolation. Response criteria are summarized in [Appendix 5](#).

7.2. Response Assessment for Subjects with FL and Other B-Cell Lymphomas

For subjects with FL, MCL, MZL, DLBCL, and high-grade B-cell lymphomas, efficacy assessments will be based on the Lugano Classification response criteria ([Cheson 2014](#)). Response criteria are summarized in [Appendix 6](#).

7.3. Response Assessment for Subjects with AML

Response assessments will be based on the European LeukemiaNet (ELN) recommendations ([Döhner 2017](#)). Response criteria are summarized in [Appendix 4](#).

8. STUDY PROCEDURES

See the Schedule of Assessments ([Appendix 1](#)) for a detailed list of study procedures and assessments for subjects with CLL/SLL, FL, MCL, MZL, DLBCL, and high-grade B-cell lymphomas. See the Schedule of Assessments ([Appendix 2](#) and [Appendix 3](#)) for a detailed list of study procedures and assessments for subjects with AML receiving voruciclib monotherapy or voruciclib + venetoclax combination therapy, respectively. Instructional details (where applicable) for procedures are contained in [Section 9](#).

8.1. Informed Consent

Each subject’s signature must be obtained on a written Informed Consent Form (ICF), which has been approved by an IRB or IEC, prior to any study-related procedures being performed. The ICF must incorporate a Release of Medical Information that authorizes release of medical records to the trial investigators, monitors, sponsor and its designees, the FDA or other regulatory authority. The ICF must be in a language fully comprehensible to the prospective subject. The consenting process must be documented in the medical chart, and a signed copy of the ICF provided to the subject.

8.2. Subject Enrollment

Prior to Amendment 11, sites submitted a Subject Enrollment Form to the sponsor or designee (e.g., contract research organization [CRO]) for approval prior to enrolling each subject in the study. The Subject Enrollment Form is no longer implemented as of Amendment 11.

8.3. Screening Period

During the screening period, the Investigator should carefully review each subject's past medical history to ensure eligibility. All inclusion and exclusion criteria should be supported by corresponding documentation in the medical records.

Screening assessments are to be performed within 28 days of first dose of voruciclib or the first dose of venetoclax in combination cohorts. Laboratory assessments need not be repeated on Day 1 if performed within the prior 72 hours. Physical examinations need not be repeated on Day 1 if performed within the prior 7 days. Some tests performed as part of routine care prior to obtaining ICF (e.g., computed tomography [CT] scan, bone marrow biopsy) may not need to be repeated for the study as long as they were performed within the allowed screening window. This avoids unnecessary repeat tests and undue burden on subjects.

The risk for TLS must be assessed and the Investigator must make sure appropriate prophylaxis has been provided (see guidelines in [Table 24](#) and [Figure 3, Appendix 9](#)).

8.4. Enrollment and Randomization

There is no randomization in this study. Once the subject has been deemed eligible, approved, and registered, the subject may enroll on study.

8.5. Cycle 1 Day 1 Tests and Administration of Voruciclib or Venetoclax

The Investigator should assess any changes in the subject's medical condition or history since the Screening visit. Any significant changes since screening should be discussed with the Medical Monitor to confirm that the subject can start study drug administration. All Cycle 1 Day 1 tests and procedures outlined in the Schedule of Assessments ([Appendix 1](#), [Appendix 2](#), and [Appendix 3](#)) must be performed prior to study drug administration. Cycle 1 Day 1 should be on Monday, if possible, so that specimens for correlative and biomarker assays can be shipped for receipt no later than a Friday.

The risk for TLS must be assessed and the Investigator must make sure appropriate prophylaxis has been followed (see guidelines in [Table 24](#), [Appendix 9](#)).

A record of the administration of the first dose of voruciclib or venetoclax (AML only) will be documented in the source documents.

Any safety laboratory tests at Cycle 1 Day 1 should be performed at the local institutional laboratory as specified on the Schedule of Assessments.

PK samples will be shipped to a central laboratory for analysis.

8.6. Treatment

The treatment phase begins on the day voruciclib or venetoclax is first administered and continues through the last day of administration. Treatment will be tracked by 28-day periods identified by a numerical cycle (e.g., Cycle 1, Cycle 2...). Response assessments for subjects with CLL/SLL, FL, MCL, MZL, DLBCL, and high-grade B-cell lymphomas, as defined in [Section 7](#), will be performed according to the Schedule of Assessments ([Appendix 1](#)) and detailed in [Appendix 5](#) and [Appendix 6](#). Response assessments for subjects with AML will be performed according to the Schedule of Assessments ([Appendix 2](#) and [Appendix 3](#)) and detailed in [Appendix 4](#).

8.7. End of Study Visit

The End of Study (EOS) visit will occur 30 days (± 3 days) from the last day of treatment drug(s) administration (or prior to starting a new treatment if urgent treatment is required). The end of treatment date and reason for discontinuation study drugs will be entered in the End of Treatment form in the EDC.

8.8. End of Study

The study will be closed when all subjects who received study drug have completed their EOS visit and all study data have been collected for analysis.

9. STUDY ASSESSMENTS

The following sections describe the methods for assessments of clinical and functional outcomes included in the trial. Refer to the Schedule of Assessments ([Appendix 1](#), [Appendix 2](#), and [Appendix 3](#)) for frequency and specific timing of assessments.

9.1. Medical History and Prior Anti-Cancer Treatment

A complete medical history will be collected during screening. Data associated with any interventional procedure, surgical operation (for any reason), and all prior cancer therapies will be collected.

9.2. Demographics

Subject demographic data including date of birth (year of birth required at a minimum), sex, race, and ethnicity will be recorded in the electronic case report forms (eCRFs).

9.3. Concomitant Medication

Data on concomitant prescription and OTC medications will be collected. This data will be recorded from 28 days prior to Day 1 of any study drug administration through 30 days after the last dose of voruciclib or venetoclax (combination cohorts), or until a subsequent anti-cancer therapy is initiated. See [Section 4.14](#) for further details regarding prohibited treatments and concomitant medications.

9.4. Physical Examination and Vital Signs

The physical examination will include the examination of all organ systems (at the Investigator's discretion, genitourinary system may be excluded). Vital sign measurements will include systolic and diastolic blood pressure, heart rate (HR), body temperature, height (Screening visit only), and weight.

A symptom-directed exam will be performed as indicated in Schedule of Assessments, and additional exams may be performed as clinically indicated.

9.5. Adverse Events

Adverse events will be collected at each visit as described in [Section 6](#).

A treatment-emergent AE (TEAE) is defined as an adverse event starting or worsening in CTCAE grade after the first dose until 30 days after the last dose of study drug(s), or start of new anti-cancer therapy, whichever is earlier. An adverse event reported ≥ 30 days after the last dose of study drug(s) will be reported and counted as TEAE if considered related to study drug and resulted in study drug discontinuation or an SAE.

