10.2. Study Endpoints

The primary study objectives are to determine the safety and tolerability and safe and mBED of voruciclib monotherapy in subjects with relapsed and/or refractory B-cell malignancies and AML and to determine the safety, tolerability and safe and mBED of voruciclib in combination with venetoclax in subjects with relapsed and/or refractory AML.

Safety will be assessed by AEs graded according to NCI CTCAE v5.0; laboratory safety tests including hematology (CBC), serum chemistry; physical examination; vital signs; ECOG performance status; and triplicate 12-lead ECG. If 2 or more of 6 subjects experience a DLT in a dose cohort, then the next lower dose will be the MTD.

The primary endpoint is:

- The incidence of AEs, including DLTs.

Secondary endpoints are:

- Efficacy endpoints within each tumor type:
 - a. Overall Response Rate (ORR), defined as the proportion of subjects who achieve a best overall response of
 - CR, CRi, or PR, with responses defined per 2008 International Workshop on CLL (IWCLL) guidelines,
 - CR or PR by 2014 Lugano criteria for non-Hodgkin lymphoma,
 - CR, CRi, CR_{MRD}, MLFS by the 2017 ELN criteria for AML
 - b. DOR defined as the time from first achieving a response to date of documented disease progression or death from any cause. Subjects who die due to any cause prior to progression will be censored
 - c. PFS defined as time from first dose of study drug to date of documented disease progression or death from any cause
 - d. Estimates of the exposure and association with efficacy and safety variables for voruciclib administered as monotherapy, and the PK of voruciclib and venetoclax when administered in combination

The exploratory endpoints are:

- a. Effects on biomarkers and functional activities of proteins in the apoptotic pathway
- b. Correlations of anti-tumor activity and baseline tumor characteristics

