- e. **EOS** - The End of Study (EOS) visit will occur 30 days (\pm 3 days) from the last day of study drug (voruciclib or venetoclax) administration or prior to starting a new treatment if urgent treatment is required.
- f. **Symptom-directed exam** – performed as indicated, and additional exams may be performed based on interim history
- g. **Vital signs** – includes systolic and diastolic blood pressure (BP), heart rate (HR), and body temperature.
- h. **Pregnancy test** – Serum pregnancy test in females of childbearing potential at screening, urine pregnancy test Day 1 of each cycle and at EOS.
- i. **HIV testing** – HIV antibody testing is required.
- j. **Hepatitis B and Hepatitis C testing** – Hepatitis B core antibody, surface antibody and surface antigen, and hepatitis C virus antibody (HCV Ab) tests are required. Hepatitis B polymerase chain reaction (PCR) is required if hepatitis B core antibody and/or surface antigen is positive. Hepatitis C PCR is required if HCV Ab test is positive.
- k. **Adverse events** – Recorded from the first dose of venetoclax and continues until 30 days after the last dose of any study drug, or until a subsequent anti-cancer therapy is initiated, whichever is earlier.
- l. **Concomitant medications** – Recorded from 28 days prior to Cycle 1 Day 1 through 30 days after the last dose of any study drug, or until a subsequent anti-cancer therapy is initiated.
- m. **ECG** – 12 lead ECGs performed in triplicate (approximately 2–5 minutes apart while the subject is resting). ECGs will be performed at screening and pre venetoclax dose on Cycle 1 Day 1. On Cycle 1 Day 3, pre voruciclib dose and 4 hours post voruciclib dose, on Cycle 1 Day 8 pre voruciclib dose, on Cycle 1 Day 14* pre voruciclib dose and 4 hours post voruciclib dose, at Cycle 2 Day 1 pre-dose voruciclib, and EOS. Additional ECGs as clinically indicated. For Cycle 1, pre-dose ECG should be within the 2 hours prior to dosing and post-dose within a 30-minute window either side of the nominal time. When a PK blood draw is scheduled at the same time as ECG, the ECG should be performed first and as close as possible immediately followed by the PK draw.
*For Cohort 12 (QOD dosing), since there is no dosing on Cycle 1 Day 14, ECGs will be performed on Cycle 1 Day 13 pre voruciclib dose and 4 hours post voruciclib dose.
- n. **CBC with differential** – WBC, ANC, RBC, Hgb, Hct, platelets, MCH, and differential.

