### 8.7.2 Adverse Events (AE)

An AE is any untoward medical event that occurs to a subject following the start of study drug administration, whether or not the event is considered drug-related. Pre-existing conditions are not considered an AE unless the condition worsens by at least one grade following the start of study drug administration. Adverse events will be captured from the first dose of study drug and continue until 30 days after the last dose, or until a subsequent anti-cancer therapy is initiated if this occurs earlier than 30 days after the last study drug dose.

Treatment-emergent adverse events (TEAEs) are defined identically as AEs in this study.

An SAE is an AE that results in any of the following outcomes:

- Death
- A life-threatening condition
- An inpatient hospitalization or prolongation of an existing hospitalization
- A persistent or significant disability/incapacity
- A congenital anomaly/birth defect
- Important medical events that may not be immediately life-threatening or result in death or hospitalization but may jeopardize the patient or may require intervention to prevent one of the other outcomes listed above

Elective hospitalizations not in response to an AE is not considered an SAE. Adverse events constituting an SAE will be reported beginning from the first dose of study drug.

All deaths within 30 days of the last dose of study drug that are an outcome of an AE should be reported. Deaths due to disease progression should be reported as such and not as SAEs..

An overview of AEs will be provided by dose cohort, disease group and in total, summarizing subject incidence of the following information:

- Any TEAEs
- Drug-related TEAEs
- CTCAE grade  $\geq 3$  TEAEs
- Drug-related CTCAE grade  $\geq 3$  TEAEs
- Deaths due to AEs
- Treatment-emergent SAEs
- Drug-related treatment-emergent SAEs

- Dose interruption due to TEAEs
- Dose interruption due to drug-related TEAEs
- Dose reduction due to TEAEs
- Dose reduction due to drug-related TEAEs
- Discontinuation of study drug due to TEAEs
- Discontinuation of study drug due to drug-related TEAEs

The number and percentage of subjects with TEAEs and Grade 3/4/5 TEAEs will be summarized for each dose cohort, tumor type, and in total by SOC and PT. For these summaries, subjects with multiple adverse events will be counted only once per SOC and PT.

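### Drug-related non-fatal SAEs that start after new anti-cancer therapy but before Day 30 fall outside both the capture rule and the TEAE rule, while the same SAE after Day 30 is inside both

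*Protocol*

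**What the plan says.** The primary endpoint in Protocol 10.2 is "The incidence of AEs, including DLTs".

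**Counting.** Protocol 9.5 gives TEAE status to events starting or worsening "after the first dose until 30 days after the last dose of study drug(s), or start of new anti-cancer therapy, whichever is earlier". It adds one exception: an event reported 30 days or more after the last dose "will be reported and counted as TEAE if considered related to study drug and resulted in study drug discontinuation or an SAE".

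**Capture of SAEs.** Under Protocol 6.4, SAEs "continue to be captured until 30 days after the last dose of study drug(s), or until a subsequent anti-cancer therapy is initiated". This sentence does not say which of the two limits prevails. The next one adds: "SAEs occurring after 30 days will be captured if believed to be related to study drug". Deaths have their own rule: "Deaths within 30 days of the administration of voruciclib or the administration of combination therapy must be reported as an SAE", unless the cause is disease progression.

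**Recording of AEs.** Appendix 3, footnote k (combination cohorts) states the earlier-of rule outright: recording "continues until 30 days after the last dose of any study drug, or until a subsequent anti-cancer therapy is initiated, whichever is earlier". Appendix 1, footnote l and Appendix 2, footnote j give the same two limits without saying which prevails.

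**SAP.** Section 8.7.2 uses the same 30-day limit for AE capture, "or until a subsequent anti-cancer therapy is initiated if this occurs earlier than 30 days after the last study drug dose". It makes TEAEs identical to AEs and contains no rule for events after Day 30.

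**The concern.** The window can close for two reasons, Day 30 or new therapy, but the related-event exception is tied to only one of them. Closing it early through new therapy therefore leaves an interval in which neither the main rule nor the exception applies. Inside that interval the protocol does not ask for a serious event that the investigator attributes to study drug, yet it asks for the same event later, when attribution is usually harder.

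AE incidence is the primary endpoint, and serious related events are the part of it that matters most in a Phase 1 study with cohorts of three to six subjects. The scheduled visits do not close the gap. Protocol 8.7 lets the End of Study visit be brought forward to before new treatment when that treatment is urgent, and 6.1 allows follow-up of related Grade 2 or higher AEs to end when subsequent therapy starts.

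**Working it through.** No sample-size or power figure is involved, so the check compares the rules by event type and onset time.

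**Example.** Take the last dose as Day 0, new therapy on Day 5, and a non-fatal SAE judged related to voruciclib.

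- Onset Day 12: the 9.5 window closed on Day 5 and its exception has not begun. The same holds for 6.4 if its two limits are read as earlier-of. The event is not captured and not counted.
- Onset Day 31: the 6.4 late sentence captures it, and the 9.5 exception counts it because it is related and an SAE.

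Both onsets fall after new therapy began, and neither late clause carries a condition about new therapy. Confounding by the next regimen therefore cannot explain why the earlier event is left out and the later one taken in.

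**All event types under the protocol:**

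| Event | Onset between new therapy and Day 30 | Onset after Day 30 | Asymmetry |
|---|---|---|---|
| Related non-fatal SAE | Not captured (6.4), not counted (9.5) | Captured (6.4), counted (9.5) | Yes |
| Related non-serious AE | Not recorded, not counted | Not counted unless it led to study drug discontinuation | Essentially none |
| Related death, not due to progression | Reportable as an SAE (6.4); outside the 9.5 count if read literally | Reportable as an SAE (6.4), counted (9.5) | None in capture |
| Unrelated event | Not captured | Not captured | None |

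**Under the SAP.** Capture stops at the earlier limit and there is no late-event clause. The Day 12 and Day 31 SAEs are both left out of the TEAE tables, so the asymmetry exists only in the protocol.

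**Length of the gap.** With new therapy d days after the last dose, gap = 30 − d days, and share of the follow-up window = (30 − d)/30. The documents give no value for d; those below are assumptions.

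- d = 7: 23 days, 23/30 = 77%
- d = 14: 16 days, 16/30 = 53%
- d = 21: 9 days, 9/30 = 30%
- d ≥ 30: no gap

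These are days closed to related SAEs, not shares of events lost.

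**The case against.** The strongest reply is that stopping safety collection at the next regimen is a deliberate attribution rule, repeated in 9.5, the appendix footnotes and SAP 8.7.2, and that this is at most loose drafting. Section 6.4 omits the earlier-of wording and elsewhere requires every SAE to be reported whatever its attribution. The 9.5 exception turns on when an event is reported, so a gap-onset SAE reported on or after Day 30 might qualify.

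Much of this stands. The cut-off is a reasonable convention for non-serious and unrelated events and should stay. The wording is ambiguous, but an ambiguity that makes capture depend on report date is itself a reason to redraft. The requirement to report SAEs regardless of attribution does not clearly override a capture period set in the same section.

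A reader might infer more than the documents support:

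- *That all related AEs show the asymmetry.* They do not; ordinary related AEs after Day 30 are not counted either.
- *That the SAP tables will show the Day 31 event but not the Day 12 one.* SAP 8.7.2 would show neither.
- *That Study Review Committee decisions rest on the incomplete TEAE tables.* No section says so. Protocol 4.3.1.1 and SAP 7.10 describe review of ongoing safety data. The DLT component is confined to Cycle 1, and Protocol 4.12 replaces subjects who leave Cycle 1 early without a DLT. A narrow overlap is conceivable for someone who starts new therapy before Day 28, but the point does not rest on it.
- *That a large share of subjects switch quickly.* The documents give no time to next therapy.
- *That drug is still present when capture stops.* Protocol 4.3.2.2 reports an average of 8 ng/mL, under 2% of maximum, seven days after the last voruciclib dose at 150 mg. In the combination cohorts the clock runs from the last dose of any study drug. A subject who completes a cycle is by Day 28 already 14 days (28 − 14) or 7 days (28 − 21) past the last voruciclib dose, depending on the schedule.
- *That the known lung and differentiation events illustrate the gap.* Those described in 4.2.1.1, 4.10 and 4.11 arose during treatment.

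**Conclusion.** The point holds for one class of event: drug-related, non-fatal SAEs with onset after new anti-cancer therapy and before Day 30. For these the protocol is wrong as written, because it excludes the event closer to dosing and includes the later one, with no reason that distinguishes them. The AE part of the primary endpoint is affected.

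This rests on reading 9.5 literally and on reading 6.4 as earlier-of, consistent with 9.5 and Appendix 3. The gap lasts 30 − d days for each affected subject. How many subjects and events that covers cannot be estimated, since the documents give neither time to new therapy nor a post-treatment event rate. The case for correcting it is the logical gap in a primary safety measure and the low cost of closing it, not a demonstrated loss of events.

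**What to change.** In Protocol 6.4 and 9.5, start the existing exception for related SAEs from whichever event closes the window. Suggested text: *An SAE with onset after the reporting window has closed, whether at 30 days after the last dose or at the start of new anti-cancer therapy, is captured and counted as a TEAE if judged related to voruciclib or venetoclax. Onset after new therapy is flagged.* Key the exception to onset date, not report date, and state in 6.4 that the earlier limit prevails.

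Align Appendix 1 footnote l, Appendix 2 footnote j, Appendix 3 footnote k and SAP 8.7.2; the SAP also needs the late related-SAE rule that it now lacks. Leave the new-therapy cut-off in place for non-serious AEs and for unrelated events. Extending capture to every related AE would reverse a consistent convention and is not needed to close this gap.

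The cost is short edits in six places, with no change to sample size or visits. The sponsor will receive a few more SAEs, with attribution confounded by the next regimen. Because concomitant-medication recording also stops at new therapy (Protocol 9.3), the SAE report should name that regimen and its start date. The flag allows TEAE summaries with and without these events.
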